A study team member and participant will meet during the participant's scheduled CTU appointment to collect their MAT tool and antiemetic/aromatherapy diary. During this interaction, the study team member will reinforce instructions and answer any participant's questions, concerns, or confusion regarding the aromatherapy inhaler, MAT tool, and antiemetic/aromatherapy diary. A new study packet and an aromatherapy inhaler, if necessary, will be provided to the participants.

Visit 3: Participants' visit three will take part on their next scheduled chemotherapy infusion – i.e., the participants' third chemotherapy cycle during their study period. A study team member

will give the participant access to complete the following assessments via iPad or laptop: postassessment and demographic form, psychological distress VAS, resilience scale, and FACIT-G.

Arm 1 - Control group:

A study team member and participant will meet during the participants' scheduled CTU appointment to collect their final MAT tool and antiemetic diary. During this interaction, the study team member will assess the participant's study experience and provide the participant with a thank you card appreciation for their study participation.

Arm 2 - Interventional group:

A study team member and participant will meet during the participants' scheduled CTU appointment to collect their final MAT tool and antiemetic/aromatherapy diary. During this interaction, the study team member will assess the participant's study experience and provide the participant with a thank you card appreciation for their study participation.

If a participant is admitted to an SCCC's inpatient unit or has their chemotherapy temporally held during their study period, the study procedures will be postponed until their next regularly scheduled outpatient CTU visit. Participants' known admissions will be noted in the respective participant's study notes.

Table 2

Timepoints	1	2	3	4
Visits	Initial	1	2	3 (Final)
Assessments collected on:				
Demographic	X*			
Pre-assessment	X*			
Psychological distress symptoms (VAS)	X*			X*
Resilience	X*			X*
FACIT-G	X*			X*
MAT tool		Х	Х	Х
Antiemetic diary		Х	Х	Х
Antiemetic/Aromatherapy diary (intervention group only)		Х	Х	Х
Post-assessment				X*

Participant's Study Period and Associated Assessments

Note: (*) indicates measures where data are entered directly in REDCap.

Interventions and Assessment Instruments:

Pre-Assessment and Demographic Checklist:

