The participants will complete a pre-assessment and demographic checklist that assesses their demographic information (e.g., race, ethnicity, age, and education level), essential oils sensitivity, and risk factors of CINV. The pre-assessment demographic checklist will provide the descriptive characteristics of the study's sample population.

• Additional data, such as medical history (e.g., diagnoses, allergies, medications, cancer history, and treatment regimen), family history, and recent outpatient and inpatient clinic or hospital visits, will be extracted from the electronic health record.

Aromatherapy Inhaler (Arm 2 – Intervention Only):

The study's aromatherapy inhaler can be used when participants' have their first sign of CINV and as needed. The aromatherapy inhaler contains a proprietary blend of peppermint, spearmint, lavender, and ginger essential oils that can last up to 6 months. Participants will twist open the cap, hold the inhaler below their nose, and take deep breaths to activate the aromatherapy inhaler. Once the participant is done, they will close the aromatherapy inhaler to turn it off. The aromatherapy vapors can be safely inhaled for as long as it takes to provide comfort and relief for the patient. There are no "limits" or duration restrictions for any essential oils in the blend. The aromatherapy inhalation amount can vary from brief intermittent use to continuous inhalation over several minutes. The aromatherapy inhaler has unlimited uses with no time limits. One inhalation of aromatherapy is equivalent to one dose. There are no known contraindications. At each study visit, the study team member will offer the participant a replacement aromatherapy inhalation device.

Antiemetic/Aromatherapy Diary (Arm 2 - Intervention Only):

The antiemetic/aromatherapy diary will allow the participants to record their weekly usage (date and time) of aromatherapy and antiemetic uses and evaluate the aromatherapy and type (name) of antiemetic medications. The evaluation will assess the effects of the aromatherapy on CINV by capturing the number of inhalations per nausea episode and asking the participants, 'Did the aromatherapy take away your nausea?' answers include: 'it took away my nausea completely' to 'it had no effect on my nausea.' If the participants cannot get relief from the aromatherapy, the participants will take the prescribed antiemetic, and the participants will document the type of antiemetic medication they needed.

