Additionally, there is a space to name other complementary methods used to relieve CINV and describe how the CINV was controlled in the antiemetic/aromatherapy diary.

MAT Tool:

The Antiemesis (MAT) tool created by the Multinational Association of Supportive Care in Cancer (Dranisaris et al., 2017) is a user-friendly and reliable tool designed to measure acute and delayed CINV across patients entire chemotherapy regimen. The MAT tool is available in English and Spanish languages. The MAT tool consists of eight items that assess participants' CINV (i.e., occurrence, duration, and frequency). Four items assess the participants' acute phase (i.e., first 24 hours after receiving chemotherapy), and the last four items assess the delayed phase (i.e., day 2 to day 4 after chemotherapy treatment). The MAT tool has been used as a communication tool to facilitate discussions about their CINV to their healthcare providers (Alafafsheh & Ahmad, 2016; Molassiotis et al., 2007; Yamaguchi et al., 2009). This MAT tool has shown good reliability and validity, with Cronbach alpha of 0.77-0.97 in 1200 patients with cancer (Alafafsheh & Ahmad, 2016; Dranisaris et al., 2017; Molassiotis et al., 2007; Yamaguchi et al., 2009).

Antiemetic Diary (Arm 1 - Control Only):

The antiemetic diary allows the participants to record their usage (date and time) and type (name) of antiemetic medications. Additionally, there is a space to name other

complementary methods used to relieve CINV and describe how the CINV was controlled in the antiemetic diary.

Resilience Scale:

The Connor-Davidson Resilience Scale (CD-RISC) will assess the participants' resilience pre and post the intervention (Burns & Anstey, 2010). For this study, we will use the 10-item questionnaire that includes questions such as: are you 'able to adapt to change,' 'can (you) deal with whatever comes,' to 'can handle unpleasant feelings.' This scale has shown good reliability and validity, with Cronbach alpha of 0.88 in 343 patients with cancer and 122 breast patients with cancer (Matzka, Mayer, Köck-Hódi, Moses-Passini, Dubey, Jahn, ... & Eicher, 2016; Scali, Gandubert, Ritchie, Soulier, Ancelin, Chaudieu, & Uddin, 2012).

Psychological Distress Symptoms:

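### Antiemetic use is self-recorded on a different diary in each arm, so a difference in recording between the forms cannot be separated from a treatment effect

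*Combined protocol and SAP*

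**What the plan says.** Section 9 (Procedures Involved, instruments) describes two diaries.

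- **Control.** The heading is "Antiemetic Diary (Arm 1 - Control Only)". The content is given as: "The antiemetic diary allows the participants to record their usage (date and time) and type (name) of antiemetic medications".
- **Intervention.** The heading is "Antiemetic/Aromatherapy Diary (Arm 2 - Intervention Only)". Participants "record their weekly usage (date and time) of aromatherapy and antiemetic uses and evaluate the aromatherapy and type (name) of antiemetic medications". The evaluation part works by "capturing the number of inhalations per nausea episode" and asks how far the aromatherapy relieved the nausea. The description continues: "If the participants cannot get relief from the aromatherapy, the participants will take the prescribed antiemetic". In that case they are asked to write down which drug it was.

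Both diaries also leave space for other complementary methods. The initial-visit and Visit 1 to 3 procedures follow the same split, with one diary per participant according to arm. Table 2 marks one row "Antiemetic/Aromatherapy diary (intervention group only)". The antiemetic diary row above it carries no arm label.

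The Study Endpoints section derives antiemetic use from a mean diary score covering frequency and type. Section 11 (Analysis of the Primary Endpoint(s)) compares the arms on it by Mixed ANOVA over Visits 1, 2 and 3. No other source is named for this endpoint, and no rule says how one score is obtained from two forms.

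**The concern.** A between-arm comparison assumes that the outcome is measured in the same way in both arms. Here the recording form is part of the allocation. Extra prompts on the combined form might make a participant record more doses. A form that mentions the antiemetic as the step after the inhaler might lead some participants to leave out doses unrelated to an inhaler episode, such as scheduled ones. Neither diary description says how scheduled and as-needed doses are told apart.

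Randomisation balances the participants, not the forms they are handed afterwards. Any capture difference goes straight into the estimated arm difference. It could create an apparent reduction in antiemetic use, hide a real one, or shrink it. Antiemetic use belongs to the primary objective and is analysed among the primary endpoints in section 11, so the comparison is a prominent one.

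**Working it through.** **Step 1. Compare the forms as described.**

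| Feature | Control diary | Combined diary |
|---|---|---|
| Date and time of antiemetic | yes | yes (described as weekly usage) |
| Name of antiemetic | yes | yes |
| Other complementary methods | yes | yes |
| Inhalations per nausea episode | no | yes |
| Relief rating for the inhaler | no | yes |
| Antiemetic also described as following insufficient relief | no | yes |
| Scheduled versus as needed | not stated | not stated |

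The core antiemetic fields match. The surrounding questions and the framing differ.

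**Step 2. Can the analysis remove a form effect?** All controls use one form and all intervention participants use the other, so form and arm are the same variable. A capture gap that is constant over visits enters the main effect of condition. One that changes over visits enters the time-by-treatment term. The Mixed ANOVA evaluates both and can adjust for neither.

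**Step 3. Illustrate the size.** The plan gives no figure to reproduce: no mean, SD, power or effect size for antiemetic use. From the documents: 100 participants in total and a type I error of 0.05. Assumed: 50 per arm (the ratio is not stated), a two-sided test, mean 6 and SD 4 doses per cycle, a common SD, no true effect, and one form missing a fraction u of doses.

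Apparent difference δ = u × 6. SE = SD × √(2/n) = 4 × √(2/50) = 0.8.

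Chance of p<0.05 = Φ(δ/SE − 1.96) + Φ(−δ/SE − 1.96).

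| u | δ | δ/SE | Normal approximation | Two-sample t |
|---|---|---|---|---|
| 5% | 0.3 | 0.375 | 0.0565 + 0.0098 = 0.0663 | 6.6% |
| 10% | 0.6 | 0.75 | 0.1131 + 0.0034 = 0.1165 | 11.5% |
| 15% | 0.9 | 1.125 | 0.2019 + 0.0010 = 0.2029 | 20.0% |
| 20% | 1.2 | 1.5 | 0.3228 + 0.0003 = 0.3231 | 31.8% |

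**Step 4. Vary the assumed spread.** Only the coefficient of variation (CV = SD/mean) matters, because δ/SE = u / (0.2 × CV). The case above has CV 4/6 = 0.67. Normal approximation:

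| CV | u = 5% | u = 10% | u = 20% | u = 30% |
|---|---|---|---|---|
| 0.5 | 0.079 | 0.170 | 0.516 | 0.851 |
| 0.75 | 0.063 | 0.102 | 0.266 | 0.516 |
| 1.0 | 0.057 | 0.079 | 0.170 | 0.323 |

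**Step 5. Three visits instead of one.** Steps 3 and 4 treat a single cycle. If the three visits are averaged with an assumed correlation of 0.5, the SD is multiplied by √((1 + 2 × 0.5)/3) = 0.816. At u = 20% the chance becomes 0.688, 0.372 and 0.232 for CV 0.5, 0.75 and 1.0. Averaging reduces noise but not a constant gap.

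**Step 6. With a common form.** If capture is equal, u = 0 and the chance is 0.025 + 0.025 = 0.05, the nominal level.

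**The case against.** The strongest reply is that the documents describe one antiemetic record with inhaler items added for the intervention arm. The opening sentence on the combined diary asks for the date, time and name of antiemetics without any condition. A reader might infer from the later sentence that intervention participants log an antiemetic only when the inhaler fails. The text does not support that: the later sentence adds to the unconditional instruction and does not replace it. The forms themselves are not reproduced in the documents, so their layout is unknown. This part of the reply stands: differential capture is possible, not shown.

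A reader might also take Table 2 to contradict the text by having the intervention arm complete both diaries. What Table 2 shows is one row without an arm label. The visit procedures and both diary headings consistently give one diary per arm, so this is a labelling gap that the rest of section 9 resolves. Read literally, Table 2 would in any case mean that both arms share the plain log.

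The rejection rates are not evidence from this trial. Mean, SD, capture gap and equal allocation are all assumed. That stands too.

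Some protection exists: staff explain the forms at the start, reinforce the diary instructions at Visits 1 and 2 in both arms, and review data weekly, including missing data. This should reduce gaps in recording, but none of it checks whether the two forms capture doses equally. It does not answer the point that the arms are compared on different instruments when they need not be.

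**Conclusion.** The point holds as a design weakness that is cheap to avoid. The two arms record the same outcome on different forms, the diary is the only named source for it, and no later analysis can separate form from treatment. The documents do not establish that a bias exists, and its direction is open.

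Under the assumptions stated in the working, a 10% to 20% capture gap would turn a nominal 5% false-positive rate into about 12% to 32%. For a 20% gap the single-cycle range is about 17% to 52% across CVs of 1.0 to 0.5. These figures show how sensitive the comparison is to a modest gap. They should not be read as an estimate of this trial's error rate. The missing label in Table 2 is a minor correction.

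**What to change.** Use one identical antiemetic log page in both arms, with date, time, drug name, and whether the dose was scheduled or as needed. State that the antiemetic-use endpoint is derived from that page only. Move the inhalation counts and relief rating to a separate page for the intervention arm. Label the Table 2 rows and the section 9 headings to match.

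The cost is a re-layout of the English and Spanish forms and IRB review of the revised versions. Intervention participants may have to enter some dates and times twice, so a small added burden cannot be ruled out. Treatment, visits and sample size do not change. Unblinded self-report remains, and so may some extra prompting from the inhaler page. For any diaries already collected on the present forms, record the form version and report the limitation.

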-

Effects of Aromatherapy on Chemotherapy-Induced Nausea and Vomiting: A Control Trial

IBIS Protocol#: 20201412

Principal Investigator	[name]., RN, MSN, LHRM, CPHQ, CCM	
	School of Nursing and Health Studies	
	University of Miami	
	[name]	
	[contact]	
	[contact]	
Funding Agency		
Version	2.0	
Version Date	09/08/2023	
NCT Number	NCT05319860	

1) **Protocol Title**

Effects of Aromatherapy on Chemotherapy-Induced Nausea and Vomiting: A Control Trial

2) IRB Review History*

Not applicable

3) Objectives*

Primary:

To investigate the effect of aromatherapy inhalation on chemotherapyinduced nausea and vomiting (CINV) and the use of antiemetics among patients with cancer receiving moderate to high emetogenic outpatient chemotherapy regimens.

Secondary:

To investigate the effect of aromatherapy inhalation on resilience, psychological distress symptoms (e.g., stress, anxiety, and depression), and quality of life among patients with cancer receiving moderate to high emetogenic chemotherapy regimens outpatient.

Aims & Hypotheses:

- (1) To investigate the effect of aromatherapy inhalation on CINV among patients with cancer receiving moderate to high emetogenic chemotherapy regimens outpatient.
 - (a) Outpatient patients with cancer using aromatherapy inhalation will reduce the discomfort associated with their CINV while receiving moderate to high emetogenic chemotherapy.
- (2) To investigate the effect of aromatherapy inhalation on the use of antiemetics among patients with cancer receiving moderate to high emetogenic chemotherapy regimens outpatient.
 - (a) Outpatient patients with cancer using aromatherapy inhalation will reduce the use of antiemetics while receiving moderate to high emetogenic chemotherapy.
- (3) To investigate the effect of aromatherapy inhalation on resilience among patients with cancer receiving moderate to high emetogenic chemotherapy regimens outpatient.
 - (a) Outpatient patients with cancer using aromatherapy inhalation will have higher levels of resilience while receiving moderate to high emetogenic chemotherapy.
- (4) To investigate the effect of aromatherapy inhalation on psychological distress symptoms of stress, anxiety, and depression among patients with cancer receiving moderate to high emetogenic chemotherapy regimens outpatient.

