- a) Primary Outcome
 - a) Outcome Measure Title: Reduction in severity of CINV
 - b) Outcome Measure Description: Assessed by the mean score of the Antiemesis (MAT) tool, which measures acute and delayed CINV across patients' chemotherapy regimens.
 - c) **Outcome Measure Timeframe**: Data tool collected during study visits 1, 2, 3, and 4.
- b) Secondary Outcome
 - a) Outcome Measure Title: Reduction in Antiemetic Use
 - b) **Outcome Measure Description**: Assessed by the mean score of antiemetics diary, which measures the usage frequency (date and time) and type (name) of antiemetic medications.
 - c) **Outcome Measure Timeframe**: Data diary collected during study visits 1, 2, 3, and 4.
- c) Exploratory Outcome
 - a) Outcome Measure Title: Improved Resilience
 - b) **Outcome Measure Description**: Assessed by the mean score of the Connor-Davidson Resilience Scale (CD-RISC), which measures the participants' resilience pre and post the intervention.
 - c) Outcome Measure Timeframe: Data collected at baseline and final visit.
- d) Exploratory Outcome
 - a) Outcome Measure Title: Reduction in Psychological Distress Symptoms
 - b) **Outcome Measure Description**: Assessed by the mean score of the psychological distress symptoms visual analog scale the patients' anxiety, stress, and depression at pre-and post-assessment.
 - c) Outcome Measure Timeframe: Data collected at baseline and final visit.
- e) Exploratory Outcome
 - a) Outcome Measure Title: Improved Quality of Life
 - b) **Outcome Measure Description**: Assessed by the mean score of Functional Assessment of Chronic Illness Therapy General (FACIT-G), which measures the

patients' quality of life and well-being at pre-and post-assessment.

c) Outcome Measure Timeframe: Data collected at baseline and final visit.

The study objectives and endpoints were selected because (a) more research is necessary to understand the effects of aromatherapy on moderate and high emetogenic chemotherapy regimens in an outpatient setting; (b) the literature suggests that CINV has a relationship with decreased quality of life and increased antiemetic usage and psychological distress symptoms; (c) the relationship between CINV and resilience has not been established. However, literature has shown a relationship between resilience and a reduction in psychological distress symptoms and improved quality of life.

9) Procedures Involved*

The study will continue as follows:

Initial visit

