The study's initial visit will occur while patients are in the CTU or fast-track area as they get ready for treatment. The entire study will be explained to the patient when they are preparing for their chemotherapy regimen in a comfortable area provided by the SCCC. After answering the potential participants' questions, the study team member will go through the study's informed consent process if the participant is interested and willing to consent. The potential participants will have time to review and discuss informed consent. After the patient signs the informed consent, the participant will be randomized to the control or the intervention arm.

On the same day, the study team member will meet the participant in the CTU while they receive their infusion and provide both the control and intervention groups, access to complete, via iPad or laptop, the electronic pre-assessment and demographic form, psychological distress VAS, resilience scale, FACIT-G, and a study packet that includes the Antiemesis (MAT) tool, antiemetic diary or antiemetic/aromatherapy diary. The study packet will be completed and returned to the study team member on the participants' next scheduled chemotherapy infusion. The study team member will explain to the participants how to use the MAT tool and how to fill the antiemetic diary or antiemetic/aromatherapy diary. The study team member will go through the instructions to ensure that they understand the forms and how to complete them.

Arm 1 - Control group:

Participants in the control group will receive standard medical care, consisting of antiemetic medicine at the first sign of CINV on a schedule as prescribed by the healthcare provider. The study team member will review with the participant how to use the weekly study packet (e.g., MAT tool and antiemetic diary) and explain that a study team member will collect the packet on their next scheduled chemotherapy infusion.

Arm 2 - Intervention group:

Participants in the intervention group will receive an aromatherapy inhaler for complementary use with their antiemetic medication. Participants will be encouraged to use the aromatherapy inhaler at the first sign of CINV before taking their antiemetic medications that are labeled "as needed". The interventional group will be instructed that one normal inhale is equivalent to one dose of aromatherapy and must report essential oils sensitivity to a study team

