Data will be stored and managed in REDCap and SPSS. The data file on the shared Box (a password-protected digital encrypted shared drive, a part of the University of Miami) will be used for analysis purposes so that all research team members have access to the most recent version of the file.

All data will be collected using study participant de-identified ID numbers to protect the confidentiality of participants. All participants will be assigned unique alphanumeric numbers as they enroll in the study. No personal identifying information will appear on any questionnaires or other material. All participant information will be de-identified at the Sylvester location. Likewise, information matching the participant number to a name or other identifying information will be kept in a password-protected shared Box folder that the study's PI and Co-PI can only access. All other participants' assessment data will be scanned into a password-protected shared Box folder labeled only with participants' ID numbers and will be entered into REDCap. REDCap database system will be used to help input participant demographics and study-related information.

Standard operating procedures specifying the rules, methods, and procedures to follow will be used and checked by the study team member. The research team members will be in weekly contact with the PI to review any data (i.e., missing data) and ensure data integrity. The Co-PI will also review all consent forms to ensure that they are complete.

Descriptive analysis will be conducted on demographic (e.g., age and gender) variables to report the characteristics of the sample. Pre- and post-assessments will be analyzed using paired t-tests for normally distributed continuous data and Wilcoxon signed-rank for non-normal continuous data. Chi-Square test of independence will be used for categorical data. Additionally, descriptive statistics and qualitative content analysis will be used to analyze data regarding ease of study.

1. General Approach

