All endpoints will be evaluated using parametric analysis to examine the difference between the two conditions across the 3-time points for primary endpoints (CINV and Use of Antiemetics) and 2-time points for secondary endpoints (resilience, psychological distress, and quality of life). The analysis will be conducted using SPSS Version 26. For binary outcomes (CINV), logistic regression will be used. For continuous outcomes (antiemetic use, resilience, psychological distress, and quality of life) a Mixed ANOVA will be used with condition as the between-subjects variable and change over time on the outcome as the within-subjects variable. Sphericity and homogeneity of variance assumptions will be tested prior to interpretation of the results, and the

Greenhouse-Geisser correction will be implemented if Sphericity is violated. A type I error rate of .05 will be used to determine significance for all analyses.

Outcome	Measure	Type of measurement
CINV	MAT	Binary
Use of antiemetics	Antiemetic Diary	Continuous
Resilience	CD-RISC	Continuous
Psychological Distress	Visual Analog Scale	Continuous
Quality of Life	FACIT-G	Continuous

2. Analysis of the Primary Endpoint(s)

For CINV, logistic regression will be used to determine whether the use of aromatherapy decreases the risk for any of the following outcomes: acute nausea, delayed nausea, acute vomiting, or delated vomiting. For use of antiemetic medication, a Mixed ANOVA will be used to evaluate differences between conditions (aromatherapy group vs. treatment as usual) across the 3-time points (Visit 1, Visit 2, and Visit 3). Time x treatment effects will be evaluated as well as main effects.

3. Analysis of the Secondary Endpoint(s)

For resilience, psychological distress, and quality of life, a Mixed ANOVA will be used to evaluate differences between conditions (aromatherapy group vs. treatment as usual) across the 2-time points (Initial visit and final visit). Time x treatment effects will be evaluated as well as main effects

4. Baseline Descriptive Statistics

Participant demographic characteristics will be analyzed using descriptive statistics. Specifically, frequencies and percentages will be reported for categorical variables, and means and standard deviations will be reported for continuous variables.

12) **Provisions to Monitor the Data to Ensure the Safety of Subjects***

This section is not applicable. The risks of this study are minimal.

13) Withdrawal of Subjects*

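### Resilience, distress and quality of life most plausibly have two unranked analyses, and the paired tests among them do not compare the arms

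*Combined protocol and SAP*

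**What the plan says.** The opening text of section 11 (Data Management), before the numbered analysis subsections, states: "Pre- and post-assessments will be analyzed using paired t-tests for normally distributed continuous data and Wilcoxon signed-rank for non-normal continuous data". It names no outcome and no arm, and does not say whether the tests are run within each arm or on all patients together.

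Subsection 1 (General Approach) then sets a different rule: "All endpoints will be evaluated using parametric analysis to examine the difference between the two conditions". It adds: "A type I error rate of .05 will be used to determine significance for all analyses". Subsection 3 is specific: "For resilience, psychological distress, and quality of life, a Mixed ANOVA will be used to evaluate differences between conditions", using the initial and final visits, and "Time x treatment effects will be evaluated as well as main effects".

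The Study Endpoints section describes FACIT-G as measuring "patients' quality of life and well-being at pre-and post-assessment". It uses the same pre/post wording for the distress VAS and close wording for CD-RISC. Section 9 repeats this in its instrument descriptions.

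The design is randomised: "the participant will be randomized to the control or the intervention arm". Aims 3 to 5 in section 3 concern the effect of aromatherapy; aim 3, for example, reads: "To investigate the effect of aromatherapy inhalation on resilience among patients with cancer receiving moderate to high emetogenic chemotherapy regimens outpatient".

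**The concern.** The same three outcomes appear to have two inferential analyses that answer different questions. A paired test asks whether scores changed between the initial and final visits. The aims ask whether aromatherapy altered that change relative to usual care. Distress, resilience and quality of life may well move over several chemotherapy cycles in everyone, so a significant change in the aromatherapy arm is not evidence of an effect.

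The two instructions also conflict on method. The Wilcoxon signed-rank test is neither parametric nor between-condition, yet General Approach requires both for all endpoints. With no stated order of precedence, the choice of result to report is left until the data have been seen.

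**Working it through.** **Which outcomes the paired sentence covers.** Table 2 shows three measures taken at both the initial and final visits: the distress VAS, CD-RISC and FACIT-G. Section 11 classes all three as continuous, which is the kind of data the sentence addresses. CINV (MAT tool) and antiemetic use are collected at Visits 1 to 3 with no baseline, so they have no pre/post pair.

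**What each analysis estimates.** Let the mean change be δ_A in the aromatherapy arm and δ_C in the control arm.
- Paired test in the aromatherapy arm: tests δ_A = 0.
- Paired test pooled over equal arms: tests (δ_A + δ_C)/2 = 0. The Mixed ANOVA main effect of time addresses the same quantity.
- Time x treatment contrast: tests δ_A − δ_C = 0. In a 2 x 2 design this is the two-sample t-test on change scores.

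Only the last compares the arms.

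**Inputs for an illustration.** From the documents: total N = 100 (section 6) and alpha .05 (section 11). Assumed, because the documents do not give them: 50 per arm (40 as a range), two-sided testing, normally distributed changes, and an equal drift in both arms of d SDs of change. Equal drift means no treatment effect. The plan states no figure of its own to reproduce.

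**Calculation.** The paired t-test has noncentrality d√n. At d = 0.3 and n = 50 this is 0.3 × √50 = 2.12, against a critical value of about 2.01 on 49 df; the exact noncentral t gives 0.548. With n = 40, 0.3 × √40 = 1.90 and the result is 0.457. Pooled over 100 patients, 0.3 × √100 = 3.0 and the result is 0.844. For the time x treatment contrast the noncentrality is zero at every d, because d − d = 0. Wilcoxon (4,000 runs) and time x treatment (20,000 runs) were simulated.

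Chance of p < 0.05 with no treatment effect:

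| Shared drift d (SD of change) | 0 | 0.2 | 0.3 | 0.4 | 0.5 |
|---|---|---|---|---|---|
| Paired t, aromatherapy arm, n = 50 | 5% | 28% | 55% | 79% | 93% |
| Wilcoxon, same arm, n = 50 | 5% | 26% | 53% | 78% | 93% |
| Paired t, aromatherapy arm, n = 40 | 5% | 24% | 46% | 69% | 87% |
| Paired t, both arms pooled, n = 100 | 5% | 51% | 84% | 98% | 99.9% |
| Time x treatment, 50 per arm | 5.1% | 5.4% | 5.0% | 4.6% | 4.9% |

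Three further results, with 50 per arm:
- The pattern in which aromatherapy is significant and control is not has probability 0.55 × 0.45 ≈ 25% at d = 0.3, although the arms behave identically.
- With zero drift, counting either the aromatherapy-arm paired test or the interaction as a positive gives 8.3% false positives. Two independent tests would give 1 − 0.95² = 9.75%.
- The paired test can also miss a real effect. If aromatherapy patients stay stable and controls worsen by 0.6 SD of change (assumed), the aromatherapy-arm paired test rejects in about 5% of trials and the time x treatment contrast in 84%.

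**The case against.** The strongest reply is that the plan already contains a valid test. Subsection 3 names these outcomes and gives them a between-condition analysis with a time x treatment term, and endpoint-specific text would normally govern over a general sentence. This stands. A reader might infer that aims 3 to 5 have no suitable analysis, and the documents do not support that. What remains is that no text ranks the two analyses or calls the paired tests descriptive, and one alpha covers them all.

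Second, the pre-assessment and post-assessment are also named forms, listed in Table 2 on rows separate from the three scales, and the sentence sits between demographics and ease-of-study data. The authors may have meant those forms, so it would be too strong to say that they cannot have. Against that reading, one form covers demographics, oil sensitivity and CINV risk factors and the other evaluates the study tools; each appears once in Table 2, and they share no described content that could be paired. The three scales are the more plausible target, but this is an inference.

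Third, it is tempting to say that the paired tests ignore the control group. The text does not go that far: control patients may be tested separately or pooled. The supported statement is that the arms are not compared.

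Fourth, 55% is not the trial's false-positive rate. It is the paired test's power to detect a real change over time under one assumed drift. It becomes an error only if that change is presented as a treatment effect, and nothing says the team will do so.

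Finally, removing the sentence takes away the plan's only provision for non-normal continuous data, so a replacement is needed.

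**Conclusion.** The point holds as a conflict between two unranked analyses of resilience, distress and quality of life, one of which cannot test the aims. The main effect of time in the Mixed ANOVA shares that limitation, and the plan lists main effects beside the interaction without saying which one answers the aim.

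The size depends on drift, which the documents do not give. Under the stated assumptions the aromatherapy-arm paired t-test ranges from 5% with no drift to 79% at 0.4 SD of change, and at 0.3 it is 55% with 50 per arm or 46% with 40. The between-arm contrast stays near 5% throughout.

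The reach is limited. The three outcomes are labelled exploratory under Study Endpoints and secondary in section 11. The analyses of CINV and antiemetic use are not touched. The plan should be corrected, but the trial's main comparison is not undermined by this point.

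**What to change.** In the opening text of section 11, state which measures the pre/post sentence refers to. Remove the paired t-test and Wilcoxon signed-rank test as inferential analyses of CD-RISC, the VAS and FACIT-G, and report change within each arm descriptively.

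In subsections 1 and 3 of section 11, name one between-arm analysis as the sole inferential test for each of these outcomes. ANCOVA of the final value on arm and baseline value is preferable: the baseline is already collected, and adjusting for it generally gains precision over change scores. The Mixed ANOVA is not invalid, so the time x treatment contrast alone would also resolve the conflict, provided the main effects are not used to judge the aims. Add a between-arm rank-based or bootstrap sensitivity analysis for use if the VAS scores are clearly non-normal.

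The cost is wording only, with no new data, visits or patients. The change should be made before outcome data are analysed by arm.
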